### 4. Sample size and power calculation

We plan to recruit and randomize 350 participants over 24 months. There should be 99% or more power to determine the direct effect of RIMO on the primary outcome of time to MAT initiation (H1a) assuming a sample size of 350 patients, randomized into two groups of 175 each, interviews at 4 time points for the main analysis (baseline, and 3, 6, and 9 months post-randomization), our average completion rate of 94+% per follow-up wave, and a moderate to large effect size of  $d=3.0$ . This expected effect size was based on the natural log of the odds ratio ( $\text{Log}^e(\text{OR})=d$ ) of initiating MAT ( $\text{OR}=20.2$ ) from RIMO Pilot study ([name] et al., under review). For the other tests of direct effects, the effective n for power calculations in repeated measures analysis varies between a lower bound of the number of unique people per group ( $N=175$  people), and an upper bound of the number of people randomized plus the completed follow-up interviews or 668 observations per group ( $O=(175 \text{ people at intake} + \text{average of } 94\% \times 175 \text{ people} \times 3 \text{ follow-ups})$ ) as a function of the intra-class correlation coefficient (ICC) associated with the individual and the number of repeated measures (RM) per person ( $\text{effective } n'=O/(1+\text{ICC}(\text{RM}-1))$ ). In our prior studies, ICC of the other dependent

variables ranged from .13 to .34. Thus the effective n= range from 429 to 398 per group and be capable of detecting an effect size of  $d=0.2$  or more with 80% power for a two-tailed test of  $p<.05$  of effect sizes  $d=.2$  or more. For mediation analysis, the tests should also have 80%+ power for a 2-tailed test of  $p<.05$  and an indirect effect size of  $d=.2$  or more.

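### Section 4's effective n of 429 to 398 per group does not follow from its own formula; with four repeated measures it is 481 to 331, and 80% power at d = 0.2 holds only up to an ICC of about .23

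*Combined protocol and SAP*

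**What the plan says.** Everything needed is in Section 4 of the combined protocol and SAP. The design is two groups of 175, with "interviews at 4 time points for the main analysis" (baseline and months 3, 6 and 9) and "our average completion rate of 94+% per follow-up wave". For the direct effects other than H1a, the section says that "the effective n for power calculations in repeated measures analysis varies between" a lower bound of 175 people per group and an "upper bound of the number of people randomized plus the completed follow-up interviews or 668 observations per group". The position between these bounds is set by the ICC and "the number of repeated measures (RM) per person", through n' = O/(1 + ICC(RM − 1)). In the team's earlier studies the ICCs of these "variables ranged from .13 to .34". The section then concludes: "Thus the effective n= range from 429 to 398 per group and be capable of detecting an effect size of" d = 0.2 or more with 80% power, two-tailed, p < .05. It nowhere gives RM a number.

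**The concern.** The formula, O and the ICC range are all stated, so a reader should be able to recover 429 and 398 by choosing the right RM. The pair is suspiciously narrow: an ICC that rises from .13 to .34 should shrink the effective sample much more than from 429 to 398.

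At stake is the power statement for the repeated-measures outcomes, which cover much of Aims 1 to 3. Both stated values lie just above the roughly 393 per group that d = 0.2 requires, so the narrow range is what makes 80% power appear to hold for every outcome. If the true lower end is well below 393, a null result on an outcome with a high ICC would be read against more power than the design has.

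**Working it through.** **Inputs (all Section 4).** 175 per group; 94% completion at each of three follow-ups; ICC .13 to .34; d = 0.2; two-sided alpha .05; n' = O/(1 + ICC(RM − 1)).

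**Step 1: O.** 175 + 0.94 × 175 × 3 = 668.5, which agrees with the plan's 668. This total includes the intake interview.

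**Step 2: can the stated pair be reproduced?** With O = 668:

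| RM | n' at ICC .13 | n' at ICC .34 |
|---|---|---|
| 2 | 668/1.13 = 591 | 668/1.34 = 499 |
| 3 | 668/1.26 = 530 | 668/1.68 = 398 |
| 4 | 668/1.39 = 481 | 668/2.02 = 331 |
| 5 | 668/1.52 = 439 | 668/2.36 = 283 |

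RM = 3 gives 398 at the upper ICC. None gives 429 at the lower ICC; to get 429 one needs an ICC of .279 with RM = 3, or .186 with RM = 4.

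**Step 3: a check that does not depend on O.** The ratio of the two endpoints is (1 + .34(RM − 1))/(1 + .13(RM − 1)), so O and the completion rate cancel. It is 1.34/1.13 = 1.19 for RM = 2, 1.68/1.26 = 1.33 for RM = 3 and 2.02/1.39 = 1.45 for RM = 4. The stated ratio is 429/398 = 1.08. No completion rate can produce the pair.

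**Step 4: which RM fits the plan.** O is built from four waves and the section names four time points. The stated lower bound is a further check: at ICC = 1 the formula should fall to about 175. RM = 4 gives 668/4 = 167, and exactly 175 at full completion (700/4). RM = 3 gives 668/3 = 223, above the plan's own lower bound.

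**Step 5: power at d = 0.2 (two-sided t-test).** About 393.4 per group are needed for 80%. The last column is the highest ICC that keeps 80% power, (O/393.4 − 1)/(RM − 1).

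| Reading | n' (ICC .13 to .34) | Power | ICC limit for 80% |
|---|---|---|---|
| RM = 4, O = 668 | 481 to 331 | 87% to 73% | .23 |
| RM = 4, O = 700 (full completion) | 504 to 347 | 89% to 75% | .26 |
| RM = 3, O = 668 (intake in O only) | 530 to 398 | 90% to 80% | .35 |
| RM = 3, O = 0.94 × 175 × 3 = 493.5 (follow-ups only) | 392 to 294 | 80% to 68% | .13 |

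In the first row, the effect detectable with 80% power is d = .18 at ICC .13 and d = .22 at ICC .34.

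**The case against.** The strongest reply is that RM = 4 is inferred. The only trace of the value actually used is the 398, and that points to RM = 3. On that reading 80% power holds up to an ICC of .35, which covers the whole range, and the one wrong number, 429, is too low (530 would follow), so it does not flatter the design. It is true that RM is unstated and that the shortfall depends on its value. But RM = 3 with O = 668 counts the intake interview as information and leaves it out of the design effect, and it breaks the plan's own lower bound of 175. When RM = 3 is paired with the follow-up observations alone, power is lower still.

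A second reply is that the simple formula is not the planned analysis. Section 10 anchors the models on the baseline value of the outcome. Assume that this means baseline adjustment, that all waves correlate equally at the ICC, and that m people per group are seen at each follow-up. Then n' = m/[(1 + 2·ICC)/3 − ICC²]. With m = 164.5 (94% of 175) this gives about 408 to 370 and power of about 81% to 78%; with m = 175 it gives 434 to 394 and 84% to 80%. So 73% may overstate the shortfall for the planned model. That stands as a caveat. It rests on assumptions that the plan does not state, it is not the formula the plan gives, and at 94% completion it still falls below 80% at ICC .34.

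It is also fair that the consequence is small and confined to outcomes other than H1a.

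**Conclusion.** The concern holds. That 429 and 398 cannot both come from the stated formula is certain: it follows from the endpoint ratio whatever O is. With RM = 4, the value that matches O, effective n is 481 to 331 per group and power at d = 0.2 is about 87% to 73%. The claimed 80% is met only up to an ICC of about .23, roughly the lower half of the stated range, and the gap is about 7 points at ICC .34.

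The size of the gap rests on RM = 4, on the plan's own design-effect formula and on 94% completion. The missing-data text (Sections 1 and 10) expects only about 90% or more; at 90%, O = 175 + 0.90 × 175 × 3 = 647.5 and n' is 466 to 321, slightly worse. The H1a power statement is a separate calculation and is not affected.

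**What to change.** State RM = 4 in Section 4 and replace the sentence with: *With RM = 4, O = 668 and ICC .13 to .34, effective n' ranges from 481 to 331 per group. Two-tailed power at d = 0.2 (p < .05) is about 87% to 73% (80% or more up to an ICC of about .23); the detectable d at 80% power is about .18 to .22.*

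If the sponsor intended another RM or a baseline-adjusted calculation, the section should state that value or formula and its assumptions, use an O that matches, and recompute both ends of the range; 429 to 398 cannot stay beside the present formula.

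The cost is one or two sentences. No participants are added and no analysis changes. The stated power becomes less favourable at the upper end of the ICC range.

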## **2. Primary and secondary objectives and outcome measures**

The primary outcome measure for the study is the GAIN-Quick Version 3 (GAIN-Q3). The GAIN-Q3 includes 4-6 symptom count screeners that are correlated .9 or more with the 11 to 43-symptom version in the full GAIN. It also has cut points with excellent (~90%) sensitivity, specificity, and area under the curve (AUC) relative to the full GAIN in 9 problem areas related to substance use disorders, physical health, internalizing and externalizing mental health disorders, as well as school, work, stress, HIV risk behaviors/victimization, and crime/violence. The days of use measures have been validated against the Timeline Follow-back, collateral reports, and urine and saliva tests. The GAIN-Q3 also includes summary measures for health care utilization, functional impairment, quality of life, and life satisfaction. The GAIN-Q3 includes the behavioral health screener and health care utilization measures that have been recommended by NIH's Phenx common data elements as two of the most reliable, valid, efficient, and inexpensive tools in the field. At each follow-up, the Q3 follow-up will be supplemented with a) a section on overdose and naloxone experiences, and b)

symptom counts from the OUD scale. Table 2.1 crosswalks the key independent measures and secondary outcomes from the hypotheses to their definitions, reliability, data sources, and the specific aims they address.

Table 2.1. Crosswalk of Variables, Definition, and Aims	H1	H2	H3
Experimental Assignment: Based on computer-generated urn randomization, participants will be assigned to the referral only control group or the experimental RIMO condition.	R	R	R
MAT Time to Initiation: Days from index naloxone administration to the initiation of any kind of MAT, from treatment records.	O		
Length of Staying on Medication: Days between MAT initiation and discharge, from treatment records.	O		
MAT Days: Total days of MAT over 9 months from GAIN-Q3 and treatment records.	O	M	M
Time to Relapse: Days from randomization to next subsequent use of opioids or heroin based on GAIN Q3 follow-up interviews and urine tests.		O	
Opioid Days of Use: Days of opioids and/or heroin use summed over the GAIN-Q3 follow-up interviews.		O	M
Opioid Overdose: Number of opioid-related overdose[s] summed over the GAIN-Q3 follow-up interviews.		O	

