Opioid Related Fatality: Any ICD-10 cause of death related to opioid overdose (T40.1, T40.2, T40.3, T40.4, T40.6, X42, X44, X62, X64, Y12, Y14) in CDC death records.		O	
Opioid Use Disorder: The average of 11 past 90-day items on the Opioid Use Disorder Scale (11 DSM-5 symptoms) self-reported from the GAIN-Q3 follow-up interviews			O
Physical Health: The average of 5 past 90-day items on the Health Problem Screener (worried about health, pain, health kept participant from meeting responsibilities) from GAIN-Q3 follow-up interviews.			O
Mental Health: The average of the past 90-day items across the Internalizing (symptoms of depression, anxiety, trauma, suicide) or Externalizing (symptoms of attention deficit, hyperactivity, conduct, gambling) Disorder			O
Cost of Health Care Utilization: Sum of the quarterly costs of health care from the GAIN-Q3 follow-up interviews; based on the frequency of health, mental health or substance-related ED visits, hospitalizations, residential treatment, outpatient surgery, MAT, intensive outpatient, outpatient treatment days/times multiplied by their respective costs using published estimates by health economists, adjusted for inflation using the CPI.			O
Key: R=Randomization, O=Outcome, M=Mediator			

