## **10. Statistical analysis plan**

Missing data. Participants will complete their baseline interview prior to randomization. Based on prior studies conducted by the applicants, it is expected that approximately 90% or more of the 3, 6, and 9-month post-randomization interviews will be completed. Among these completed interviews, prior studies conducted by the team indicate that less than 1% will have additional missing data on any of the core items required to test the study hypotheses. Multiple imputations will be used to replace the small amounts of missing data to allow the least biased estimate for each analysis. To further reduce potential bias, analyses will be rechecked by running them without missing data. If there are any clinically significant differences ( $d > |.2|$ ), a general latent variable framework will be used to analyze non-ignorable or systematic missing data that tests whether missing data is qualitatively different by condition.

Survival Analysis for Time to MAT Initiation and Time on Medication (Aim 1). The primary outcome is the days from randomization until the initiation of any kind of MAT. Relative to the referral only control group, the direct effects of RIMO on reducing the days from randomization to initiation of any MAT (H1a) and increasing the days on medication after initiation (H1b) will be evaluated with a Cox Regression model using IBM SPSS version 24 with random assignment to RIMO as the main predictor, as the investigators have done in earlier experiments. It will be examined after the point of randomization and after each follow-up interview. Survival analysis incorporates information about censorship (e.g., death, people who were not admitted to MAT within 9 months) and can incorporate covariates if needed. The output includes a case summary (e.g., missing data, other problems, descriptive statistics) and an evaluation of each term (e.g., beta, its standard error, Wald, its probability, the odds ratio, the 95% confidence interval for the odds ratio). The beta can also be converted to a Cohen's effect size *d*. All analyses will use an intent-to-treat approach (i.e., participants are analyzed as assigned regardless of their actual level of participation in RIMO). We will also conduct a secondary analysis of the time to MAT initiation after each RIMO checkup to understand the pattern over time as we have done with earlier experiments.

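### The blanket claim of 80% power at d=0.2 for the non-primary outcomes does not follow from Section 4's own formula, counts baseline observations, and leaves the unit of analysis and the scale of d unsettled

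*Combined protocol and SAP*

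**What the plan says.** Section 4 assumes 350 participants "randomized into two groups of 175 each", with "interviews at 4 time points for the main analysis" (baseline and 3, 6 and 9 months) and "our average completion rate of 94+% per follow-up wave". For all direct effects other than H1a it takes "668 observations per group" (175 at intake plus 94% of 175 at each of three follow-ups) and divides by 1 + ICC(RM-1), where RM is the number of repeated measures per person. The ICC range from prior studies is .13 to .34. Its conclusion, for 80% power and a two-sided 5% test, is: "Thus the effective n= range from 429 to 398 per group and be capable of detecting an effect size of" at least d=0.2. It names 175 people per group as the lower bound of effective n but gives no power there, and it does not say which SD d refers to.

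Table 2.1 in Section 2 defines opioid days as "Days of opioids and/or heroin use summed over the GAIN-Q3 follow-up interviews" and cost as "Sum of the quarterly costs of health care from the GAIN-Q3 follow-up interviews". Overdoses are likewise summed over the follow-up interviews, and MAT days are a total over 9 months. Each is one number per person.

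Section 10, in the paragraphs on direct effects, plans a multilevel model for these same four outcomes, with repeated observations nested in participants and anchored on the baseline value. Its missing-data paragraph uses a lower completion figure than Section 4: "it is expected that approximately 90% or more of the 3, 6, and 9-month post-randomization interviews will be completed".

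**The concern.** One power statement covers outcomes of different structure, and it can be checked against the inputs printed beside it. Three things do not fit: the printed effective n against its formula, the inclusion of baseline among observations that are meant to carry the treatment contrast, and the definition of four outcomes as totals when the calculation counts them as repeated measures.

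The statement covers, among others, total MAT days (H1d), opioid days (H2b), overdoses (H2c) and cost (H3e). MAT days and opioid days are also the planned mediators. If true power is below the stated 80%, a non-significant result on these outcomes carries less information than a reader of Section 4 would suppose. The primary outcome, time to MAT initiation, is powered separately and is not affected.

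**Working it through.** **Method.** Two-sample comparison of means, two-sided 5%. Power is approximately Phi(d x sqrt(n/2) - 1.96), with n per group. The noncentral t gives the same results to within about 0.2 points. For 80% power at d=0.2, n = 2 x (1.96 + 0.8416)^2 / 0.2^2 = 392.4, so 393 per group.

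**Step 1: the plan's own figure.** O = 175 + 0.94 x 175 x 3 = 668.5 and RM = 4.

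- ICC .13: 668.5 / (1 + 3 x .13) = 668.5 / 1.39 = 481. Power = Phi(0.2 x sqrt(240.5) - 1.96) = Phi(1.14) = 87%.
- ICC .34: 668.5 / (1 + 3 x .34) = 668.5 / 2.02 = 331. Power = Phi(0.2 x sqrt(165.5) - 1.96) = Phi(0.61) = 73%.

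The printed 429 and 398 are not reproduced. The 398 appears with ICC .34 and RM = 3 (668.5 / 1.68 = 397.9), although O counts four measures. The 429 does not come from ICC .13 with RM = 3 (530.6) or RM = 4 (480.9). The last step is sound: taking 429 and 398 as given, power is 83% and about 80%. The fault lies in the effective n. By the plan's formula, power falls below 80% when 668.5 / (1 + 3 x ICC) is under 393, which means an ICC above (668.5/393 - 1)/3 = .23.

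**Step 2: follow-ups only, d=0.2 in single-wave SDs.** Baseline precedes randomization, so the treatment contrast rests on three waves.

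- Unadjusted effective n = 3 x 175 x f / (1 + 2 x ICC), where f is completion.
- With baseline as a covariate, and assuming the same correlation (the ICC) between every pair of waves, the variance of the three-wave mean falls from (1 + 2 x ICC)/3 to (1 + 2 x ICC)/3 - ICC^2. Effective n = 175 x f divided by that variance. At ICC .34, for example, it is 0.56 - 0.1156 = 0.4444, and 164.5 / 0.4444 = 370.

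| Completion | ICC | Unadjusted n | Power | Adjusted n | Power |
|---|---|---|---|---|---|
| 94% | .13 | 392 | 80% | 408 | 81% |
| 94% | .34 | 294 | 68% | 370 | 78% |
| 90% | .13 | 375 | 78% | 391 | 80% |
| 90% | .34 | 281 | 66% | 354 | 76% |

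**Step 3: one total per person, d=0.2 in SDs of the total.**

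- Unadjusted: 46% at 175 per group and 44% at 164.5 (94%). The detectable d at 80% power is 0.30 to 0.31. At 157.5 per group (90%), power is about 42-43% and the detectable d is 0.32.
- Baseline-adjusted: the squared correlation between baseline and total is ICC^2 / ((1 + 2 x ICC)/3), which is .040 at ICC .13 and .206 at ICC .34. Dividing n by one minus this gives 164 (157.5 per group, ICC .13) up to 221 (175 per group, ICC .34), and power of about 44% to 55%.

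**Step 4: why the scale of d matters.** A difference of 0.2 single-wave SDs at each follow-up becomes 0.2 x sqrt(3 / (1 + 2 x ICC)) in SDs of the three-wave total: 0.31 at ICC .13 and 0.27 at ICC .34. Testing that on totals reproduces the unadjusted results of Step 2. Summing does not by itself lose power. Steps 2 and 3 differ because d=0.2 means a different effect in each.

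**The case against.** A reader might infer from Table 2.1 that these four outcomes simply have about 45% power. The documents do not support that as a settled figure. Section 10 plans a multilevel model of repeated observations for the same outcomes, and Section 4's repeated-measures calculation agrees with that model. An ICC-based formula also suggests, without saying so, that d is on the single-wave scale. The 44-46% is therefore conditional on analysing the totals, unadjusted, with d in SDs of the total.

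Nor should 66-80% be taken as the plan's by-wave power. Section 10 anchors the model on baseline. If that is read as covariate adjustment, most of the shortfall goes: about 81% to 78% at 94% completion. With all 175 per group contributing in full, an upper bound, the adjusted range is 84% to 80% (effective n 434 to 394). Multiple imputation is planned, but imputed values do not restore all the missing information. For MAT days the gain from baseline is probably small, because entrants must have been out of treatment for the past 30 days.

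These outcomes are also non-primary, Section 4 does name 175 as the lower bound, and nothing in the plan says that null results will be read as absence of effect.

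All of this limits the size of the problem. It does not explain 429 and 398, justify counting baseline as outcome data, or settle the disagreement between Table 2.1 and Section 10.

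**Conclusion.** The claim of 80% power at d=0.2 for all other direct effects is not supported across the plan's stated ICC range. The firmest part needs no outside assumption: the plan's formula and inputs give 481 to 331 per group and 87% to 73% power. Counting follow-ups only, by-wave power at 94% completion lies between 68% and 80% unadjusted and about 78% to 81% adjusted, so the shortfall may be only a few points if the baseline-anchored model is used. It would be large, with power of about 44-46% unadjusted or 44-55% adjusted, only if the totals in Table 2.1 are what is tested and d=0.2 is in their SDs. The documents do not say which applies.

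These figures assume approximately normal outcomes, equal correlation across waves, and ICCs within .13 to .34. Section 10 allows for count or zero-inflated models, for which power would differ. The point does not show that the trial is too small, and it does not touch the primary outcome.

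**What to change.** - For each outcome, state whether it is analysed by wave or as a 9-month total, and make Table 2.1 and Section 10 agree.
- State the SD in which d is expressed.
- Replace 429 to 398 with an effective n built from the three follow-ups only, with baseline as a covariate. Show the correlation assumed, and use one completion figure (or both 94% and 90%) in Sections 4 and 10.
- Restate power at d=0.2, or the detectable d at 80% power, for each outcome across the ICC range, with and without baseline adjustment. For any outcome kept as a total on its own SD, the unadjusted detectable d is about 0.30 to 0.31.

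This is a change of text and figures. It needs no extra patients, visits or data. The cost is that the stated power becomes less favourable for some outcomes.

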**TRIAL MANAGEMENT**

[figure not shown]

**6. Planned enrollment timetable**

Exhibit 6.1 shows the expected recruitment per quarter and cumulatively for the RIMO R33.

**7. Target population distribution (gender, minorities, etc.)**

Based on ambulance responses involving one or more naloxone administrations to reverse opioid overdoses within the Austin and Englewood neighborhoods, there were 946 encounters (79 per month) with people age 18 or older in 2016. Based on this data, we expect to recruit 14 to 16 people per month and that the participants will be: 25% female; 12% Hispanic; 72% Black, 15% White, 13% more than one race, and less than 1% other; and 99% were age 21 or older. Note that in the pilot study (n=33) the sample was 27% female, 15% Hispanic, 67% Black, 9% White, and 24% reporting other or multiple races.

